12.3 Screening Period

No study procedure will be completed until the subject has given written informed consent.

The Screening Period (up to 21-days before the first study check in at Day 00) aims to evaluate if subjects are eligible for the study according to inclusion/exclusion (I/E) criteria. The reasons for screening failures will be documented. subjects will perform the following procedures in the Screening Period:

- The ICF (subjects will sign an ICF prior to executing all other activities)
- Demography
- Dermatological assessment to check for potential dermatological disorder at the patch application site
- Medical / surgical history collection
- Abdominal ultrasound if deemed necessary by the investigator
- Details of Alcohol/Tobacco/Sensitivity/blood donation history
- Physical examination
- Karnofsky score
- Vital signs: pulse rate, respiration rate, sitting blood pressure and body temperature will be examined. It will be repeated if any vital sign falls outside the normal range and is considered potentially clinically significant.
- Weight, height and BMI
- Average pain over last 24-hours on 0-10 score NRS see section 19.5.
- 12-Lead ECG
- Haematology, blood chemistry (fasted), and urinalysis
- Serology testing (HBsAg, anti-HIV, anti-HCV, and syphilis antibody)
- Urine drug screen (opioids, barbiturates, amphetamines, cocaine metabolites, methadone, benzodiazepines, phencyclidine, methamphetamine, or cannabinoids) and alcohol breath test
- Blood β-HCG test for female subjects up to less than one-year post-menopause
- AEs collection after the ICF acquisition
- Collection of prior and concomitant medication and non-pharmacological therapies
- Inclusion/Exclusion criteria list will be checked when all the results of examinations are available.

Subjects who do not meet the inclusion/exclusion criteria are not permitted to attend the study. Throughout the study, subjects will be reminded to immediately report AEs experienced to the medical staff. These will be recorded in the AE section of eCRF and reported according to Section 13.3.

12.4 Re-Screening Instructions

Subjects who do not meet the criteria for study entry can be re-screened if there is an indication that the reason for exclusion has changed. Any screening measurements that fall outside of the 21-day window must be repeated and subjects must meet the study entry criteria during these

assessments. A new subject screening number will be assigned each time a subject is rescreened and the subject must be re-consented. Any subject re-screening judged by investigator should be informed and agreed by sponsor.

12.5 Randomisation

Randomisation will be completed once all inclusion and exclusion criteria are verified. Refer to Section 13.5 for further details on the treatment assignment.

12.6 Treatment and Sampling Period

Refer to section 12.8 for the food restrictions during the study.

12.6.1 Check-in Visit (Day 00)

The check-in visit (Day 00) aims to further confirm eligibility to continue in the study. At Day 00 if the subjects meet all I/E criteria, they will be randomized into one of the 3 treatment arms. Subjects will complete all the following examinations:

- Subjects will report to the study unit on the day at least 15 hours before the scheduled study drug dosing.
- Physical examination
- Average pain over last 24-hours on 0-10 score NRS see section 19.5.
- Alcohol breath test and urine drug screen; the results must be negative before IMP application in each period
- Urine β-HCG test for female subjects before menopause and less than one year after menopause and the results must be negative prior to IMP application.
- Subjects will be asked whether they have taken any prescribed or over the-counter medications, or any vitamins or mineral supplements or herbal products since their last visit, and whether they have abstained from alcohol and strenuous exercise within 48 hours before the scheduled study drug dosing. I/E criteria will be verified again to notice any changes
- 12-Lead ECG
- Vital signs (pulse rate, respiration rate, sitting blood pressure and body temperature) will be executed within 30 minutes before taking naltrexone
- At 13 hours (± 5 minutes) before the study drug dosing, 50 mg of naltrexone tablet will be administered with 150 mL water in a standing position
- AE collection
- Concomitant medications and non-pharmacological therapies
- Inclusion/Exclusion criteria list will be checked when all the results of examinations are available.

12.6.2 Three-day application period

12.6.2.1 Day 01

• Vital signs (pulse rate, respiration rate, sitting blood pressure and body temperature) will be obtained every 12 hours, within 30 min prior to the dosing of naltrexone.

- 50 mg of naltrexone tablet will be administered twice a day (every 12 hours) with 150 mL water in a standing position, the first dosing at 1 hour (± 5 minutes) before the IMP application and the second at 11 hours (± 5 minutes) after IMP application.
- Pre-dose PK sampling: a blood sample (6 mL) drawn within 30 minutes before the IMP application.
- Based on the randomization schedule, either 20 mg or 40 mg BUP TDS will be applied respectively (see section 13 for details of IMP application).
- Observe patch adhesion status immediately after patch applied and 12 hours (±1 hour) later and assess whether additional taping is required.
- Post-dose PK sampling: a blood sample (6 mL) will be drawn at 12 hours after patch application. Blood sample collection will be performed ± 2 minutes of scheduled time post dose. Every effort should be made to ensure accurate sampling time and deviations should be kept to a minimum.
- AE collection.
- Collection of concomitant medication and non-pharmacological therapies.

12.6.2.2 Day 02 and Day 03

- Vital signs (pulse rate, respiration rate, sitting blood pressure and body temperature) will be obtained within 30 min prior to the dosing of naltrexone.
- 50 mg of naltrexone tablet will be administered twice a day (every 12 hours) with 150 mL water in a standing position, with a time window of ±5 min based on scheduled time.
- A blood sample (6 mL) will be drawn at:
 - Day 02: 24-hours after patch application
 - Day 03: 48-hours after patch application

Blood sample collection will be performed ± 2 minutes of scheduled time post dose. Every effort should be made to ensure accurate sampling time and protocol deviations should be kept to a minimum.

- Observe patch adhesion status twice a day (every 12 hours ± 1 hours) and assess whether additional taping is required.
- AE collection.
- Collection of concomitant medication and non-pharmacological therapies.

12.6.2.3 Day 04

- Vital signs (pulse rate, respiration rate, sitting blood pressure and body temperature) will be obtained within 30 min prior to each dosing of naltrexone.
- 50 mg of naltrexone tablet will be administered twice a day (every 12 hours) with 150 mL water in a standing position, with a time window of ±5 min based on scheduled time.
- Observe patch adhesion status once, just before patch removal.
- BUP TDS will be removed.
- BUP patch will be removed 72 hours (±2 minutes) after being applied.
- Prior to IMP removal PK sampling: PK blood sampling to occur in the last 2 minutes of dosing i.e. within 2 minutes before the patch is removed, a blood sample (6 mL) will be drawn.

- A blood sample (6 mL) will be drawn at 73, 74, 76 and 84 hours after administration of patch with a time window of ± 2 minutes for 73-76 hours and ±1 hour for 84 hours. Every effort should be made to ensure accurate sampling time and deviations should be kept to a minimum.
- Dermatological examination of patch application site will be conducted within 0.5 hour after patch removal using a 0 7 skin status scale refer to section 19.6.
- AE collection.
- Collection of concomitant medication and non-pharmacological therapies.

12.6.2.4 Day 05 and Day 07

- Vital signs (pulse rate, respiration rate, sitting blood pressure and body temperature) will be obtained in the morning within 30 minutes prior to PK blood sampling.
- A blood sample (6 mL) will be drawn at:
 - Day 05: 96 hours after patch application
 - Day 06: 120 hours after patch application.
 - Day 07: 144 hours after patch application.

Blood sample collection will be performed \pm 1 hour of scheduled time post dose. Every effort should be made to ensure accurate sampling time and deviations should be kept to a minimum.

- Dermatological examination of patch application site will be conducted in the morning of D05 and D06 using a 0 7 dermal response score (section 19.6). In case that the result of the examination conducted at D05 is judged "No evidence of irritation", the examination scheduled for D06 will not be conducted. In case AE was reported for the skin reaction and not recovered at D06, more examinations may be needed for the AE follow-up.
- AE collection.
- Collection of concomitant medication and non-pharmacological therapies.

12.6.2.5 Day 08

- A blood sample (6 mL) will be drawn at 168 hours after patch application. Blood sample
 collection will be performed ± 1 hour of scheduled time post dose. Every effort should be
 made to ensure accurate sampling time and deviations should be kept to a minimum.
- AE collection.
- Collection of concomitant medication and non-pharmacological therapies.
- The following procedures will only be conducted for 3-day application on Day 08 of the third period, or early termination:
 - Physical examination and weight
 - Vital signs (pulse rate, respiration rate, sitting blood pressure and body temperature), within 30 minutes prior to the PK sampling.
 - 12-Lead ECG
 - Urine β-HCG test for female subjects before menopause and less than one year after menopause
 - Haematology, blood chemistry (fasted), and urinalysis

Following completion of the above procedures, the subject will complete the blood collection visit.

12.6.3 Four-day application

12.6.3.1 Day 01

- Vital signs (pulse rate, respiration rate, sitting blood pressure and body temperature) will be obtained within 30 min prior to each dosing of naltrexone.
- 50 mg of naltrexone tablet will be administered twice a day (every 12 hours) with 150 mL water in a standing position, the first dosing at 1 hour (± 5 minutes) before the IMP application and the second at 11 hours (± 5 minutes) after IMP application.
- Pre-dose PK sampling: a blood sample (6 mL) drawn within 30 minutes before the IMP application.
- Based on the randomization schedule, 40 mg BUP TDS will be applied (see section 13 for details of IMP application).
- Observe patch adhesion status immediately after patch applied and 12 hours (±1 hour)
 later, and assess whether additional taping is required.
- Post-dose PK sampling: a blood sample (6 mL) will be drawn at 12 hours after patch application. Blood sample collection will be performed ± 2 minutes of scheduled time post dose. Every effort should be made to ensure accurate sampling time and deviations should be kept to a minimum.
- AE collection.
- Collection of concomitant medication and non-pharmacological therapies.

12.6.3.2 Day 02, Day 03 and Day 04

- Vital signs (pulse rate, respiration rate, sitting blood pressure and body temperature) will be obtained within 30 min prior to each dosing of naltrexone.
- 50 mg of naltrexone tablet will be administered twice a day (every 12 hours) with 150 mL water in a standing position, with a time window of ±5 min based on scheduled time.
- A blood sample (6 mL) will be drawn at:
 - Day 02: 24 hours after patch application
 - Day 03: 48 hours after patch application
 - Day 04: 72 hours after patch application

Blood sample collection will be performed strictly according to scheduled nominal time and within \pm 2 minutes of scheduled time post dose; every effort should be made to ensure accurate sampling time and deviations should be kept to a minimum.

- Observe patch adhesion status twice a day (every 12 hours ±1 hour) and assess whether additional taping is required.
- AE collection.
- Collection of concomitant medication and non-pharmacological therapies.

12.6.3.3 Day 05

- Vital signs (pulse rate, respiration rate, sitting blood pressure and body temperature) will be obtained within 30 min prior to each dosing of naltrexone.
- 50 mg of naltrexone tablet will be administered twice a day (every 12 hours) with 150 mL water in a standing position, with a time window of ±5 min based on scheduled time.
- Observe patch adhesion status once, just before patch removal.
- BUP patch will be removed 96 hours (±2 minutes) after being applied.
- Prior to IMP removal PK sampling: PK blood sampling to occur in the last 2 minutes of dosing i.e. within 2 minutes before the patch is removed, a blood sample (6 mL) will be drawn.
- A blood sample (6 mL) will be drawn at 97, 98, 100 and 108 hours after administration of patch, with a time window of ± 2 minutes for 97-100 hours and ±1 hour for 108 hours.
 Every effort should be made to ensure accurate sampling time and deviations should be kept to a minimum.
- Dermatological examination of patch application site will be conducted within 0.5 hour after patch removal using a 0 – 7 skin status scale – refer to section 19.6.
- AE collection.
- Collection of concomitant medication and non-pharmacological therapies.

12.6.3.4 Day 06 and Day 08

- Vital signs (pulse rate, respiration rate, sitting blood pressure and body temperature) will be obtained in the morning within 30 minutes prior to PK blood sampling.
- A blood sample (6 mL) will be drawn at:
 - Day 06: 120 and 132 hours after patch application
 - Day 07: 144 hours after patch application.
 - Day 08: 168 hours after patch application.

Blood sample collection will be performed ± 1 hour of scheduled time post dose. Every effort should be made to ensure accurate sampling time and deviations should be kept to a minimum.

- Dermatological examination of patch application site will be conducted in the morning of D06 and D07 using a 0 – 7 dermal response score (refer to section 19.6). In case that the result of the examination conducted at D06 is judged "No evidence of irritation", the examination scheduled for D07 will not be conducted. In case AE was reprized for the skin reaction and not recovered at D07, more examinations may be needed for the AE follow-up.
- AE collection.
- Collection of concomitant medication and non-pharmacological therapies.

12.6.3.5 Day 09

- A blood sample (6 mL) will be drawn at 192 hours after patch application. Blood sample
 collection will be performed ± 1 hour of scheduled time post dose. Every effort should be
 made to ensure accurate sampling time and deviations should be kept to a minimum.
- AE collection.

- Collection of concomitant medication and non-pharmacological therapies.
- The following procedures will only be conducted for 4-day application on Day 08 of the third period, or early termination:
 - Physical examination and weight
 - Vital signs (pulse rate, respiration rate, sitting blood pressure and body temperature), within 30 minutes prior to the PK sampling.
 - 12-Lead ECG
 - Urine β-HCG test for female subjects before menopause and less than one year after menopause
 - Haematology, blood chemistry (fasted), and urinalysis.

Following completion of the above procedures, the subject will complete the blood collection visit.

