3 CLINICAL PROTOCOL SUMMARY

Name of Company: Mundipharma (China) Pharmaceutical Co., Ltd.										
Name of Finished Product: Buprenorphine Transdermal Patch 20 mg and 40 mg	Name of Active Ingredient: Buprenorphine									
Protocol No.: BUP14-CN-101	<eudract><ind> No.: N/A</ind></eudract>									

Registration: https://register.clinicaltrials.gov

Short Title of the Study: A single dose PK study of Buprenorphine Transdermal Patch (20 mg, 40 mg application for 3 days and 40 mg application for 4 days) in Chinese subjects with chronic pain.

Full Title of the Study: An open-label, randomized, single-dose, parallel-group study to investigate the pharmacokinetic profile of single dose Buprenorphine transdermal patch 20 mg applied for 3 days, 40 mg applied for 3 days and 40 mg applied for 4 days in Chinese subjects with chronic pain.

Objectives:

Primary

To evaluate the pharmacokinetic (PK) profile of buprenorphine and its primary metabolite, norbuprenorphine of single dose buprenorphine transdermal patch (BUP TDS) 20 mg applied for 3 days, 40 mg for 3 days and 40 mg for 4 days.

Secondary

To evaluate the safety and tolerability following a single application of BUP TDS.

Sample size and Investigator(s)/Site(s):

[figure not shown]
Total sample size of 45 subjects (15 subjects/arm) will be randomised to receive IMP with the aim to have at least 36 subjects (12 subjects/arm) completing the study and providing valid PK data. The study will be conducted in 1-3 sites in China.

Summary of Study Design:

This is an open-label, randomised, single-dose, 3 arms study design. Subjects will be randomised into one of 3 arms, in a 1:1:1 ratio, wearing BUP TDS 20 mg for 3 days or 40 mg for 3 days or 40 mg for 4 days.

Study Diagram

20mg/3d = BUP TDS 20 mg application for 3 days 40mg/3d = BUP TDS 40 mg application for 3 days 40mg/4d = BUP TDS 40 mg application for 4 days

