9.2 Safety Endpoints

Subjects will be closely monitored throughout the study for evidence of any AE. Vital signs, including pulse rate, respiration rate, sitting blood pressure and body temperature, will be measured at regular intervals. Furthermore, examinations including physical examination, 12-

lead ECG as well as laboratory parameters, will be performed on the day of the last blood sample taken.

[figure not shown]

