15.1 General Considerations

In general, continuous data will be summarised by dose group using the following descriptive statistics: number of non-missing observations (n), mean, standard deviation, median, minimum and maximum. Categorical data will be summarised by dose group as the number and percentage of subjects in each category.

In general, baseline is defined as last value prior to first dose of IMP of each period.

All details of statistical methods and analyses will be documented in the Statistical Analysis Plan (SAP).

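### Section 12.6.3.5 puts the 4-day arm's exit tests on Day 08 of a third period; the trial has one period, and the rest of the protocol points to Day 09

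*Combined protocol and SAP*

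**What the plan says.** The full title describes "An open-label, randomized, single-dose, parallel-group study to investigate the pharmacokinetic profile of single dose Buprenorphine transdermal patch", and section 13.3 has one patch applied on the morning of Day 01.

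Section 12.6.3.5, headed Day 09, covers the last visit of the 4-day arm. It states "A blood sample (6 mL) will be drawn at 192 hours after patch application" and then introduces the exit tests with "The following procedures will only be conducted for 4-day application on Day 08 of the third period, or early termination". The list is physical examination and weight, vital signs, 12-lead ECG, urine pregnancy test, haematology, chemistry and urinalysis.

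The parallel text for the 3-day arms, section 12.6.2.5 (headed Day 08, with a 168 h sample), reads "The following procedures will only be conducted for 3-day application on Day 08 of the third period, or early termination".

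Other places fix the timing as follows:
- Section 9.2, on the physical examination, 12-lead ECG and laboratory tests: "lead ECG as well as laboratory parameters, will be performed on the day of the last blood sample taken".
- Table 1.2 marks weight, pregnancy test, laboratory tests, physical examination and ECG on D09, with no mark on D08. Table 1.1 marks the same items on D08.
- Section 12.1 sends the ECG and the safety blood and urine samples to the time points in section 12.2, that is, to these tables.
- Section 12.6.3.4 has the entry "Day 08: 168 hours after patch application" for the 4-day arm and lists no ECG or laboratory tests for that day.

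Multi-period wording also remains in section 12.6.1 ("the results must be negative before IMP application in each period"), in section 12.8.1 (meal times) and in section 15.1 ("In general, baseline is defined as last value prior to first dose of IMP of each period").

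**The concern.** This is an operative scheduling instruction, and for the 4-day arm it cannot be followed together with Table 1.2. The protocol allows one to three sites, and sections 15.3 and 17.3 require strict adherence. A site working from 12.6.3.5 and a site working from Table 1.2 could test the same arm on different days, and one of them would deviate whichever text is taken as binding.

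Sections 15.7.3 and 15.7.5 summarise laboratory values and ECG findings by dose group. If the 4-day arm were tested a day early, differences between dose groups in those tables would be mixed with differences in time since patch removal.

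**Working it through.** **Inputs.** Patch removal is at 72 h (3-day arms) and 96 h (4-day arm), from section 13.3. The last samples are at 168 h and 192 h, from sections 12.6.2.5 and 12.6.3.5. The average terminal half-life is 20-27 h, and decline starts about 1 h after removal, both from section 7.2. Application is on Day 01 at 0 h.

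**Step 1: reproduce the plan's own day labels.** Study day = hours/24 + 1.
- 3-day arms: 168/24 + 1 = 8, matching the Day 08 heading and Table 1.1.
- 4-day arm: 192/24 + 1 = 9, matching the Day 09 heading and Table 1.2.
- Day 08 in the 4-day arm is therefore the 168 h visit, not the last-sample visit.

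**Step 2: hours from removal to the exit tests.**
- 3-day arms, Day 08: 168 − 72 = 96 h.
- 4-day arm, Day 09: 192 − 96 = 96 h.
- 4-day arm, Day 08: 168 − 96 = 72 h.

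Tables 1.1 and 1.2 thus give equal washout in all three arms. The Day 08 wording in 12.6.3.5 would break that by 24 h.

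**Step 3: share of the removal-time buprenorphine level left.** Assuming first-order decline from removal, share = 0.5^(h / half-life).

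| Hours since removal | Half-life 20 h | Half-life 27 h |
|---|---|---|
| 96 | 0.5^4.80 = 3.6% | 0.5^3.56 = 8.5% |
| 72 | 0.5^3.60 = 8.2% | 0.5^2.67 = 15.7% |

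Ratio of the 72 h to the 96 h share: 2^(24/20) = 2.30 and 2^(24/27) = 1.85. Absolute gap: 8.2 − 3.6 = 4.6 and 15.7 − 8.5 = 7.2 percentage points. If decline starts 1 h after removal (h = 95 and 71), the shares are 3.7-8.7% and 8.5-16.2%, which changes nothing of substance.

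**Step 4: the passages side by side.** For the 4-day arm, one phrase says Day 08. The heading above it, the 192 h sample in the same section, Table 1.2, section 9.2 and section 12.1 (through the tables) all lead to Day 09. Section 12.6.3.4 already lists Day 08 vital signs, so an exit list that includes vital signs would duplicate them if it belonged to Day 08. For the 3-day arms, Day 08 agrees with all the other places and only the reference to a third period is wrong.

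**The case against.** The strongest reply is that this is a clerical slip which the protocol already resolves. Section 12.1 refers ECG and safety sampling to section 12.2, section 12.7.1 refers end-of-study procedures to Tables 1.1 and 1.2, and the disputed sentence stands under a Day 09 heading. Read fully literally, a third period never arrives and completers would have no exit tests, so the 72 h scenario keeps half of a faulty phrase and drops the other half. The residual levels compared are small, the ECG summary counts only clinically significant findings, and the laboratory tables are descriptive.

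Most of this stands. It lowers the chance that a site would test on Day 08, and it means that no material distortion of the tables is demonstrated. It does not remove the contradiction from a binding schedule. The each-period phrases are less serious: with one application, each has only one sensible reading.

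Two stronger readings are tempting, and the documents support neither as an error.
- *Exit tests and peak exposure.* No ECG or laboratory test is scheduled for completers during wear, or near the average tmax of 60-80 h. A reader might infer a flawed safety assessment. However, no passage draws a peak-exposure conclusion from the exit tests, and adverse events and twice-daily vital signs cover wear.
- *Adverse events during and after naltrexone.* The tables in 15.7.2 do not split events by onset relative to naltrexone dosing, and a reader might infer that the tolerability summary is invalid. This is at most a gap in the protocol's planned tables. Section 15.1 defers details to a separate SAP whose text is not in the supplied document. The last dose is also a debatable cut-off, because it marks when a tablet has just been taken, not when cover ends.

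**Conclusion.** The concern holds as a contradiction in the written schedule. Section 12.6.3.5 conflicts with its own heading and sample time, with Table 1.2, and with sections 9.2 and 12.1. Both 12.6.2.5 and 12.6.3.5 refer to a period that does not exist. The conflict over the day affects the 4-day arm only.

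If the Day 08 wording were followed, that arm would be tested 72 h rather than 96 h after removal, with 1.9 to 2.3 times the residual share, a gap of about 5-7 percentage points of the removal-time level. These figures assume first-order decline and the protocol's average half-lives. They illustrate unequal washout and do not estimate any effect on ECG or laboratory results. The consequence is conditional on a site following the text over Table 1.2. The PK endpoint and the sample size are unaffected.

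**What to change.** Reconcile sections 12.6.2.5 and 12.6.3.5 with section 9.2 and Tables 1.1 and 1.2, so that the exit tests fall on the day of the last blood sample in every arm. Delete the third-period reference in both sections and the leftover multi-period wording in 12.6.1, 12.8.1 and 15.1.

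The cost is a written amendment under section 17.1, with no added visits, samples or procedures.

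Optional, and not the correction of an error: a descriptive listing of treatment-emergent event onset relative to naltrexone dosing, with the cut-off stated in advance. Section 14.3 names onset date only, and the last naltrexone dose is in the evening of the removal day. The listing would therefore need onset time, or a stated rule for events starting on that date. With 15 subjects per arm, counts would be small.
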